9.2 Endpoints

Primary outcome measures:

- The safety and tolerability of xisomab 3G3 will be evaluated versus pre-treatment and placebo by reviewing number and severity of adverse events and use of concomitant medications, physical examination, vascular access site reaction, bleeding time, and changes in vital signs, ECGs, and clinical laboratory evaluations.

Secondary outcome measures:

- PD using dose-dependency of drug potency, determined by measuring changes in coagulation parameters, and thrombus accumulation (assessed and ranked by visual inspection) within the dialyzer cartridges and total protein accumulation in the HD filter after xisomab 3G3-treatment versus pre-treatment and placebo.
- Efficacy on hemodialysis efficiency using BUN and potassium levels before and after hemodialysis, length of HD, measurement of urea removed by 3 hours of dialysis, and total dialysate urea (single pool Kt/V and URR) after xisomab 3G3-treatment versus pre-treatment and placebo.

Other outcome measures:

- PK parameters of xisomab 3G3, calculated, as appropriate: AUC0-t, AUC0-inf, AUC%extrap, Cmax, Tmax, Kel, t^{1/2}, CL, and Vss.
- Development of immunity or antibodies against xisomab 3G3 after drug exposure.

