13.2.5 Vascular Access Site Reaction Assessment

The monitoring of AEs will pay special attention to vascular access fistula (or AV graft) site reactions. The preferred vascular access is an established AV fistula (or AV graft). Well established and reaction-free AV graft is an alternative, but less preferred access option, as it is more prone to complications. Patients who are hemodialyzed through catheters are not included in the study. Therefore, inspection of the AV fistula (or AV graft) and surrounding area will be performed. Any new abnormal findings inconsistent with past skin injuries as expected in patients on chronic HD will be reported as AEs. AV fistula (or AV graft) site reactions will be evaluated as outlined in the Study Events Flow Chart ([Section 6](#)). Prior to HD, the AV fistula (or AV graft) site will be examined for inflammation, infection, or flow abnormalities. When scheduled postdose, injection site examinations will be performed within approximately 20 minutes after completion of the HD session. Reactions will be rated according to the FDA Guidance for Industry: Toxicity Grading Scale for Healthy Adult and Adolescent Volunteers Enrolled in Preventive Vaccine Clinical Trials ([FDA Guidance 2007](#)) as follows:

| Local Reaction | Mild (Grade 1) | Moderate (Grade 2) | Severe (Grade 3) |
|-----------------------|---|---|--|
| Pain | Does not interfere with activity | Repeated use of non-narcotic pain reliever > 24 hours or interferes with activity | Any use of narcotic pain reliever or prevents daily activity |
| Tenderness | Mild discomfort to touch | Discomfort with movement | Significant discomfort at rest |
| Erythema/Redness* | 2.5 – 5 cm | 5.1 – 10 cm | > 10 cm |
| Induration/Swelling** | 2.5 – 5 cm and does not interfere with activity | 5.1 – 10 cm or interferes with activity | > 10 cm or prevents daily activity |

* In addition to grading the measured local reaction at the greatest single diameter, the measurement should be recorded as a continuous variable.

** Induration/swelling should be evaluated and graded using the functional scale as well as the actual measurement.

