14.3.1 Safety and Tolerability Analyses

All safety data will be populated in the individual CRFs. All safety data will be listed by patients.

The placebo patients from all cohorts will be pooled into a single placebo group for all summaries and presentations

Dosing dates and times will be listed by patient.

Incidence and time of bleeding from the HD access sites on the AV fistula (or AV graft), as described in [Section 13.2.6](#), will be counted and recorded. Treatment versus pre-treatment, placebo, and post-treatment results will be compared.

AEs will be coded using the most current version of Medical Dictionary for Regulatory Activities (MedDRA®) available at Celerion and summarized by treatment (2 active dose levels and pooled placebo) for the number of patients reporting the treatment emergent adverse event (TEAE) and the number of TEAEs reported. A by-patient AE data listing including verbatim term, coded term, treatment, severity, and relationship to study drug will be provided.

Safety data including ECGs, vital signs assessments, clinical laboratory results and vascular access site reaction, will be summarized by treatment (2 active dose levels and pooled placebo) and point of time of collection.

Descriptive statistics using appropriate summary statistics will be calculated for quantitative safety data as well as for the difference to baseline, when appropriate. In addition, a shift table describing out of normal range shifts will be provided for clinical laboratory results.

Concomitant medications will be listed by patient and treatment (2 active dose levels and pooled placebo) and coded using the most current version of WHO drug dictionary available at Celerion. Medical history will be listed by patient.

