### **8.9 Vascular Access Site Reaction**

Vascular access site reaction will be assessed at predose on Day 1 and end of HD on Days 1, 3 and 5. Any new abnormal findings inconsistent with past skin injuries as expected in patient on chronic HD will be reported as AEs.

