## **9. SUMMARY OF CHANGES FROM PROTOCOL-PLANNED ANALYSIS**

The length of HD was 3 hours in the protocol and should be approximately 4 hours. The samples collected for BUN and potassium will be at the end of dialysis (approximately 4 hours).

The analyses described in this SAP are aligned with those analyses described in the protocol.

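### SAP 8.9 plans no summary of the graded vascular access site reactions, although protocol 14.3.1 requires one, and SAP Section 9 does not declare the departure

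*SAP*

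**What the plan says.** Protocol 9.2 defines the primary outcome as safety and tolerability against pre-treatment and placebo. After the number and severity of AEs, it names "use of concomitant medications, physical examination, vascular access site reaction, bleeding time, and changes in vital signs, ECGs, and clinical laboratory evaluations". SAP 2.2 repeats this definition.

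Protocol 13.2.5 sets out the assessment: "Reactions will be rated according to the FDA Guidance for Industry: Toxicity Grading Scale for Healthy Adult and Adolescent Volunteers". The table there gives Grades 1 to 3 for pain, tenderness, erythema/redness and induration/swelling. For erythema, in addition to the grade, "the measurement should be recorded as a continuous variable". Induration is to be judged by function and by actual measurement.

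Protocol 14.3.1 gives the planned analysis: "Safety data including ECGs, vital signs assessments, clinical laboratory results and vascular access site reaction, will be summarized by treatment", and the same sentence adds the time of collection. It also states: "All safety data will be listed by patients".

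SAP 8.9 consists of two sentences. The first is the schedule: "Vascular access site reaction will be assessed at predose on Day 1 and end of HD on Days 1, 3 and 5". The second is the reporting route: "Any new abnormal findings inconsistent with past skin injuries as expected in patient on chronic HD will be reported as AEs".

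SAP Section 9 declares one change, on dialysis length and the timing of the BUN and potassium samples, and then says: "The analyses described in this SAP are aligned with those analyses described in the protocol".

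**The concern.** The protocol plans three things for this component: grading, a summary by arm and time, and AE reporting of new abnormal findings. The SAP carries forward the schedule and the AE reporting but not the summary, while stating that nothing else has changed.

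Protocol 13.2.5 asks that AE monitoring pay special attention to access site reactions, and protocol 8.5 says the hemostatic safety of the drug in ESRD patients on hemodialysis is not yet known. If the SAP is followed as written, a reader of the report could see which reactions became AEs. That reader would have no table showing how many patients were examined and had no reaction, how grades for each sign moved across visits, or how post-dose findings compare with the predose examination.

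**Working it through.** No figure of the plan is at issue, so the check compares commitments with planned outputs.

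**1. Is a summary specified in the SAP text?** Comparing SAP 8.9 with its neighbours:

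| SAP section | Summary stated? |
|---|---|
| 8.4 Laboratory tests | Yes, by time point and treatment, with change from baseline and shift tables |
| 8.5 Vital signs | Yes, by arm and time point, with change from baseline |
| 8.6 ECG | Yes, by arm and time point, with change from baseline |
| 8.9 Vascular access site reaction | No |
| 8.10 Bleeding time | Yes, by treatment and time point |

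Protocol 14.3.1 names ECGs, vital signs, laboratory results and access site reaction together in one sentence. The first three received a summary in the SAP; the fourth did not.

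**2. Is there a named output?** Counting the entries in SAP Sections 10.1 to 10.3:

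- In-text tables: 1 (10-1) + 8 (11-1 to 11-8) + 5 (12-1 to 12-5) = 14. For access site reaction: 0.
- Section 14 tables: 2 (14.1) + 26 (14.2) + 16 (14.3) = 44. For access site reaction: 0.
- Section 16 appendices: 39. For access site reaction: 0. The nearest, Appendix 16.2.5.8.2, has a shell for circuit pressures, blood flow, time to hemostasis and filter collection.

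**3. What reaches the report by other routes?**

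- *Listing.* SAP Section 8 says all CRF data will be listed by subject and time point. Grades and diameters entered on the CRF fall under this rule even without a named appendix.
- *AE tables.* New abnormal findings become AEs. If treatment-emergent, they are counted by arm, with pooled placebo alongside (Table 14.3.1.1), and by severity grade (Table 14.3.1.3). Protocol 13.2.8.3 bases AE severity on the same FDA guidance as the local reaction scale, so the grade can carry over.

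**4. What is in no planned summary?** SAP 8.3 summarizes treatment-emergent AEs only, as a percentage of subjects dosed. This leaves out:

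- the Day 1 predose finding, and so the comparison with pre-treatment;
- grade by sign and by visit;
- the number assessed at each visit with no reaction;
- the measured diameters;
- findings judged consistent with past skin injuries, which need not be reported as AEs.

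**5. Is the departure declared?** No. SAP Section 9 covers only dialysis length and sampling time.

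**The case against.** The case for leaving the SAP alone has real substance.

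- *The data would still be listed.* A reader might infer from the missing table that the graded data would never be reported. The CRF-listing rule in SAP Section 8 contradicts that. SAP Section 12 also warns that its listing shells may not cover every aspect of the study. This stands.
- *A placebo comparison exists.* A reader might infer that no comparison is possible. Reactions reported as treatment-emergent AEs are tabulated by arm and grade beside pooled placebo. This stands for those reactions, but not for the comparison with pre-treatment.
- *The AE route is the protocol's own.* Protocol 13.2.5 contains the rule that SAP 8.9 repeats, and protocol 8.4.1 describes the primary endpoint as the number of adverse events. This stands, but protocol 14.3.1 asks for the summary as well.
- *The index is incomplete.* A programmer note in SAP 11.3 refers to a Section 14.3 bleeding time table that Section 10.2 does not list. Absence from the index is therefore weak evidence taken alone. Bleeding time, however, has a summary stated in SAP 8.10 and an in-text Table 12-5; access site reaction has neither.
- *The lost information is easy to overcount.* Multiplying signs, visits and patients gives a number of possible cells, not of lost results. Protocol 13.2.5 asks before dialysis for an examination for inflammation, infection or flow abnormalities and does not clearly require all four signs to be graded then. The printed scale starts at Grade 1.
- *An amendment is not automatic.* Protocol 14.3 lets the SAP modify the plan and requires an amendment only for major modifications of the primary endpoint's definition or analysis. The definition is unchanged, and omission of one descriptive table is not shown to be major.

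**Conclusion.** The concern holds in a limited form, and its severity is minor. One of eight named primary-outcome components lacks the summary by treatment and time that protocol 14.3.1 requires. No output in SAP Sections 10.1 to 10.3 is named for it, and Section 9 states an alignment that is not true of this item. The loss is one of summary: what is missing is grade by sign and visit, no-reaction counts, diameters and the pre-treatment comparison. The documents do not support a conclusion that the data go unreported, that treated patients cannot be compared with placebo at all, or that an amendment is mandatory.

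This rests on two assumptions. The first is that the SAP would be programmed as written, without an unplanned table being added later. The second is that the CRF captures the grades and measurements that protocol 13.2.5 calls for; the CRF itself is not among the documents.

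**What to change.** Add to SAP 8.9 and Section 10.2 one Section 14.3 table of reaction grade, including a *none* category, by sign, arm and time point: the Day 1 predose finding as recorded, and end of HD on Days 1, 3 and 5. Show the number assessed at each time point, the worst post-dose grade by arm, and the shift from predose to worst grade where a predose grade was recorded. Add a named Section 16 listing with grades and measured diameters to Section 10.3.

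If AE-only reporting is intended, say so in SAP Section 9, give the reason, and correct the alignment statement. Whether the change counts as major under protocol 14.3 can be judged at that point.

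The cost is one table and one listing from data the protocol already requires, or a few sentences in Section 9. If the CRF records a grade only when a reaction is present, the *none* counts would have to be derived from the record that the assessment was done.

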### **8.10 Bleeding Time**

The time to clot (bleeding time) will be recorded following hemodialysis after the needle is removed from the vascular access site on Days -7, -5, -3, 1, 3, 5 and 12. Summary statistics will be calculated for time to clot by treatment and assessment timepoint.

### **8.11 Medical History**

All medical and surgical histories recorded in the study will be coded with MedDRA®, Version 21.1. and listed.

### **8.12 Immunogenicity**

Development of antibodies against the study drug will be evaluated by determining the anti-drug antibody (ADA) titer.

Blood samples will be collected from each subject for ADA detection prior to dosing on Day 1 and at the end of HD on Day 12. Immunogenicity testing will be done at Celerion, Lincoln, Nebraska.

Summary counts of positive and negative ADA detection will be presented by collection time and treatment.

## **9. SUMMARY OF CHANGES FROM PROTOCOL-PLANNED ANALYSIS**

The length of HD was 3 hours in the protocol and should be approximately 4 hours. The samples collected for BUN and potassium will be at the end of dialysis (approximately 4 hours).

The analyses described in this SAP are aligned with those analyses described in the protocol.

## **10. SUMMARY TABLES AND FIGURES**

Summary tables and figures are numbered following the International Conference on Harmonization (ICH) structure but may be renumbered as appropriate during the compilation of the tables and figures for the CSR. Note that all PK, PD, immunogenicity and Safety summary tables and figures will be generated using SAS®

Version 9.3 or higher and/or using Phoenix® WinNonlin® Version 7.0 or higher for summary PK TFLs, as appropriate.

## 10.1 In-text Summary Tables and Figures

The following is a list of table and figure titles that will be included in the text of the CSR. Tables and figures will be numbered appropriately during compilation of the CSR.

### Section 10:

Table 10-1 Subject Disposition Summary

### Section 11:

Table 11-1 Demographic Summary

Table 11-2 Summary of Plasma Xisomab 3G3 Pharmacokinetics Following a Single IV Infusion of 0.25 and 0.5 mg/kg Xisomab 3G3 (Pharmacokinetic Population)

### Efficiency of HD:

Table 11-3 Summary of Difference Between Pre- and Post-dialysis BUN and URR – Days -7 to 12 (Safety Population)

Table 11-4 Summary of Difference Between Pre- and Post-dialysis Potassium – Days -7 to Summary 12 (Safety Population)

Table 11-5 Summary of Kt/V Values (Safety Population)

### Drug Potency:

Table 11-6 Summary of Difference Between Pre- and Post-dialysis aPTT – Days -7 to 12 (Safety Population)

Table 11-7 Summary of Clotting in the Drip Chamber – Days -7 to 12 (Safety Population)

Table 11-8 Summary of Clotting in the Dialysis Filter – Days -7 to 12 (Safety Population)

### Figures

Figure 11-1 Arithmetic Mean Plasma Xisomab 3G3 Concentration Versus Time Following a Single IV Infusion of 0.25 and 0.5 mg/kg Xisomab 3G3 (Linear Scale) (Pharmacokinetic Population)

Figure 11-2 Arithmetic Mean Pre- and Post-dialysis BUN Values – Days -7 to 12 (Linear Scale) (Safety Population)

Figure 11-3 Arithmetic Mean Pre- and Post-dialysis Potassium Values – Days -7 to 12 (Linear Scale) (Safety Population)

- Figure 11-4 Arithmetic Mean aPPT Values Versus Time Following a Single IV Infusion of 0.25 and 0.5 mg/kg Xisomab 3G3 and Placebo (Pooled) – Day 1 (Linear Scale) (Safety Population)
- Figure 11-5 Arithmetic Mean aPPT Values Versus Time During the Course of the Study – Days -7 to 12 (Linear Scale) (Safety Population)
- Figure 11-6 Arithmetic Mean aPPT Change From Baseline Versus Time Following a Single IV Infusion of 0.25 and 0.5 mg/kg Xisomab 3G3 and Placebo (Pooled) – Day 1 (Linear Scale) (Safety Population)
- Figure 11-7 Arithmetic Mean pre- and Post-dialysis aPTT Values – Days -7 to 12 (Linear Scale) (Safety Population)

### **Section 12:**

- Table 12-1 Adverse Event Frequency by Treatment - Number of Subjects Reporting the Event (% of Subjects Dosed)
- Table 12-2 Summary of Difference Between Pre- and Post-dialysis PT – Days -7 to 12 (Safety Population)
- Table 12-3 Summary of Difference Between Pre- and Post-dialysis INR – Days -7 to 12 (Safety Population)
- Table 12-4 Summary of Difference Between Pre- and Post-dialysis PT/INR – Days -7 to 12 (Safety Population)
- Table 12-5 Summary of Post-dialysis Bleeding Time – Days -7 to 12 (Safety Population)

## **10.2 Section 14 Summary Tables and Figures**

The following is a list of table and figure titles that will be included in Section 14 of the report. Table and figure titles may be re-numbered as appropriate during the compilation of the report.

### **14.1 Demographic Data Summary Tables**

The following is a list of table and figure titles that will be included in Section 14 of the report. Table and figure titles may be renumbered as appropriate during the compilation of the report.

Table 14.1.1 Summary of Disposition (Safety Population)

Table 14.1.2 Summary of Demographics (Safety Population)

### **14.2 Pharmacokinetic and Pharmacodynamic Data Summary Tables and Figures**

#### **Pharmacokinetic Tables and Figures**

#### **14.2.1. Plasma Pharmacokinetic Xisomab 3G3 Tables and Figures**

- Table 14.2.1.1.1 Plasma Xisomab 3G3 Concentrations (ng/mL) Following a Single IV Infusion of 0.25 mg/kg Xisomab 3G3 (Pharmacokinetic Population)
- Table 14.2.1.1.2 Plasma Xisomab 3G3 Concentrations (ng/mL) Following a Single IV Infusion of 0.5 mg/kg Xisomab 3G3 (Pharmacokinetic Population)
- Table 14.2.1.1.3 Plasma Xisomab 3G3 Concentrations (ng/mL) Following a Single IV Infusion of Placebo (Pooled)
- Table 14.2.1.1.4 Plasma Xisomab 3G3 Pharmacokinetic Parameters Following a Single IV Infusion of 0.25 mg/kg Xisomab 3G3 (Pharmacokinetic Population)
- Table 14.2.1.1.5 Plasma Xisomab 3G3 Pharmacokinetic Parameters Following a Single IV Infusion of 0.5 mg/kg Xisomab 3G3 (Pharmacokinetic Population)
- Table 14.2.1.1.6 Intervals (Hours) Used for Determination of Plasma Xisomab 3G3 Kel Values (Pharmacokinetic Population)
- Figure 14.2.1.2.1 Arithmetic Mean (SD) Plasma Xisomab 3G3 Concentration Versus Time Profiles Following a Single IV Infusion of 0.25 and 0.5 mg/kg Xisomab 3G3 (Linear Scale) (Pharmacokinetic Population)
- Figure 14.2.1.2.2 Arithmetic Mean Plasma Xisomab 3G3 Concentration Versus Time Profiles Following a Single IV Infusion of 0.25 and 0.5 mg/kg Xisomab 3G3 (Linear Scale) (Pharmacokinetic Population)
- Figure 14.2.1.2.3 Arithmetic Mean Plasma Xisomab 3G3 Concentration Versus Time Profiles Following a Single IV Infusion of 0.25 and 0.5 mg/kg Xisomab 3G3 (Semi-Log Scale) (Pharmacokinetic Population)

#### **Pharmacodynamic/Immunogenicity Tables and Figures**

##### **14.2.2 BUN Tables and Figures**

- Table 14.2.2.1.1 Individual and Mean Difference Between Pre- and Post-dialysis BUN Values (unit) and URR – Days -7 to 12 – 0.25 mg/kg Xisomab 3G3 on Day 1 (Safety Population)
- Table 14.2.2.1.2 Individual and Mean Difference Between Pre- and Post-dialysis BUN Values (unit) and URR – Days -7 to 12 – 0.5 mg/kg Xisomab 3G3 on Day 1 (Safety Population)

Table 14.2.2.1.3 Individual and Mean Difference Between Pre- and Post-dialysis BUN Values (unit) and URR – Days -7 to 12 – Placebo (Pooled) (Safety Population)

**Programmer Note:** *For Tables 14.2.2.1.1 through 14.2.2.1.3, the difference will be calculated as follows: (Pre-dialysis – Post-dialysis).*

Figure 14.2.2.2.1 Arithmetic Mean Pre- and Post-dialysis BUN Values – Days -7 to 12 (Linear Scale) (Safety Population)

Figure 14.2.2.2.2 Arithmetic Mean (SD) Pre- and Post-dialysis BUN Values – Days -7 to 12 (Linear Scale) (Safety Population)

### 14.2.3 Potassium Tables and Figures

Table 14.2.3.1.1 Individual and Mean Difference Between Pre- and Post-dialysis Potassium Values (unit) – Days -7 to 12 – 0.25 mg/kg Xisomab 3G3 on Day 1 (Safety Population)

Table 14.2.3.1.2 Individual and Mean Difference Between Pre- and Post-dialysis Potassium Values (unit) – Days -7 to 12 – 0.5 mg/kg Xisomab 3G3 on Day 1 (Safety Population)

Table 14.2.3.1.3 Individual and Mean Difference Between Pre- and Post-dialysis Potassium Values (unit) – Days -7 to 12 – Placebo (Pooled) (Safety Population)

**Programmer Note:** *For Tables 14.2.3.1.1 through 14.2.3.1.3, the difference will be calculated as follows: (Pre-dialysis – Post-dialysis).*

Figure 14.2.3.2.1 Arithmetic Mean Pre- and Post-dialysis Potassium Values – Days -7 to 12 (Linear Scale) (Safety Population)

Figure 14.2.3.2.2 Arithmetic Mean (SD) Pre- and Post-dialysis Potassium Values – Days -7 to 12 (Linear Scale) (Safety Population)

### 14.2.4 Kt/V Tables

Table 14.2.4.1.1 Individual and Mean Kt/V Values (unit) – 0.25 mg/kg Xisomab 3G3 on Day 1 (Safety Population)

Table 14.2.4.1.2 Individual and Mean Kt/V Values (unit) – 0.5 mg/kg Xisomab 3G3 on Day 1 (Safety Population)

Table 14.2.4.1.3 Individual and Mean Kt/V Values (unit) – Placebo (Pooled) (Safety Population)

### 14.2.5 aPTT Tables and Figures

Table 14.2.5.1.1 Individual and Mean aPTT Values (unit) During the Course of the Study (Days -7 to 12) and Following a Single IV

	Infusion of 0.25 mg/kg Xisomab 3G3 on Day 1 (Safety Population)
Table 14.2.5.1.2	Individual and Mean aPTT Values (unit) During the Course of the Study (Days -7 to 12) and Following a Single IV Infusion of 0.5 mg/kg Xisomab 3G3 on Day 1 (Safety Population)
Table 14.2.5.1.3	Individual and Mean aPTT Values (unit) During the Course of the Study (Days -7 to 12) and Following a Single IV Infusion of Placebo (Pooled) on Day 1 (Safety Population)
Table 14.2.5.1.4	Individual and Mean aPTT Change From Baseline Values (unit) Following a Single IV Infusion of 0.25 mg/kg Xisomab 3G3 on Day 1 (Safety Population)
Table 14.2.5.1.5	Individual and Mean aPTT Change From Baseline Values (unit) Following a Single IV Infusion of 0.5 mg/kg Xisomab 3G3 on Day 1 (Safety Population)
Table 14.2.5.1.6	Individual and Mean aPTT Change From Baseline Values (unit) Following a Single IV Infusion of Placebo (Pooled) – Day 1 (Safety Population)

